12.7.2 Inferential Analysis

An analysis of covariance (ANCOVA) will be conducted by product use. The PK parameters will be transformed in the natural logarithmic scale. The model will include terms for sequence, period and product liking by the VAS-liking assessment. The results of this analysis will be presented by product in terms of:

- The percentage of variance explained by product liking by the VAS-liking assessment

Confidentiality Statement

Data and information contained in this document are considered to constitute trade secrets and confidential commercial information, and the legal protections provided to such trade secrets and confidential information are hereby claimed under the provisions of applicable law. No part of this document may be publicly disclosed without the written consent of Philip Morris Products S.A.

- The standardized effect of product liking by the VAS-liking assessment on the endpoint, defined as the mean effect divided by the square root of its variance.

Another analysis of covariance (ANCOVA) will be conducted similarly at the exception that it will be performed overall using mixed effects ANCOVA where the model will include additionally the subject as a categorical random effect to model the within subject correlations.

Confidentiality Statement

Data and information contained in this document are considered to constitute trade secrets and confidential commercial information, and the legal protections provided to such trade secrets and confidential information are hereby claimed under the provisions of applicable law. No part of this document may be publicly disclosed without the written consent of Philip Morris Products S.A.

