6.5 Statistical Analysis of PK Parameters

6.5.1 Main analysis

A mixed model analysis of variance (ANOVA) will be performed on the natural log (ln)-transformed nicotine PK parameters AUC_{0-2min} , AUC_{0-4min} , AUC_{0-Tmax} , AUC_{0-10h} , AUC_{0-last} , $AUC_{0-infinity}$, $\max(C_t/t)_{t \in [0, Tmax]}$ and C_{max} .

The model will include terms for sequence, period, product exposure as fixed effects and subject as a categorical random effect modeling the within subject correlations.

The results of this analysis for each of are presented in terms of geometric least square ratios and 95% confidence intervals for the P4M3 Gen 2.0:Cigarettes ratio.

This approach is consistent with the guidelines in the European Medicines Agency's guidelines for bioequivalence investigations and FDA's Center for Drug Evaluation and Research.

Philip Morris Products S.A.
P4M3 Gen 2.0, P4-PK-04-US

██████████ Statistical Analysis Plan Number CA34617

The analysis of T_{max} will be performed by conducting a Wilcoxon signed rank test and calculating the median T_{max} for each product along with the Hodges-Lehmann estimate of the median difference between products, and the related 95% CI.

The ANOVA analysis will be performed using the following SAS code:

```
PROC MIXED data=<> method=REML;
class subject sequence period product;
model log(parameter) = sequence period product/ddf=KR;
repeated product / subject=subject type=csh;
lsmeans product / pdiff=control("CC") cl alpha=0.05;
run;
```

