7.3 Inferential Analysis

An analysis of covariance (ANCOVA) will be conducted by product use. The PK parameters will be transformed in the natural logarithmic scale. The model will include terms for sequence, period and product liking by the VAS-liking assessment. The effect of VAS-liking will be analyzed in different models with VAS-liking at T_1 (after 4 minutes), T_2 (after 10 minutes), and T_3 (after 15 minutes). The results of this analysis will be presented by product in terms of:

- The percentage of variance explained by product liking by the VAS-liking assessment.
- The standardized effect of product liking by the VAS-liking assessment on the endpoint, defined as the mean effect divided by the square root of its variance.

The ANCOVA analysis will be performed using the following SAS code:

```
PROC MIXED data=<> method=type3;  
By product;  
class subject sequence period;  
model log(PK parameter) = sequence period liking_score/ddfm=KR solution;  
run;
```

Another analysis of covariance (ANCOVA) will be conducted similarly to the above with the exception that it will be performed overall using mixed effects ANCOVA where the model will include, in addition, the subject as a categorical random effect to model the within subject correlations.

The same model will also be used to perform the analysis for human puffing topography parameters (total number of puffs, total puff volume, and total puff duration) to estimate the effect of VAS-liking score on the topography parameters.

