Table 15.2.2.2.1 will have the following format, and Table 15.2.2.2.1.1 a similar format:

Table 15.2.2.2.1 Summary of Subscale Scores of ABOUT - Product Experience Questionnaire (PK Population)

Subscale	Statistics	Product		
		CA35	CM35	Cigarettes
P4M3 Gen 2.0				
Satisfaction	n	X	X	X
	Mean	X.X	X.X	X.X
	SD	X.XX	X.XX	X.XX
	CV%	X.X	X.X	X.X
	SEM	X.XX	X.XX	X.XX
	Minimum	XX	XX	XX
	Q1	X.X	X.X	X.X
	Median	X.X	X.X	X.X
	Q3	X.X	X.X	X.X
	Maximum	XX	XX	XX
	95% CI	XX-XX	XX-XX	XX-XX

CA35 = P4M3 Gen 2.0 Classic Auburn

CM35 = P4M3 Gen 2.0 Classic Menthol

SD = Standard deviation, CV% = Coefficient of variance, SEM = Standard error of mean, Q1 = 1st quartile, Q3 = 3rd quartile

CI = Confidence interval

PK Population = Subset of the safety population including all randomized subjects without major protocol deviations impacting the evaluability of the main objectives and for whom at least one nicotine PK parameter can be derived

Program: /CAXXXX/sas_prg/stsas/tab/ ADaM_program_name.sas DDMMYY YYYY HH:MM Status: DRAFT (Page X of Y)

Programmer Note: All subscales will be included in the summary table.

Philip Morris Products S.A.
P4M3 Gen 2.0, P4-PK-04-US

████████ Statistical Analysis Plan Number CA34617

Tables 15.2.2.2.2 and 15.2.2.2.3 will have the following format, and Tables 15.2.2.2.2.1 and 15.2.2.2.3.1 a similar format:

Table 15.2.2.2.2 Summary of VAS Craving Assessment (PK Population)

Scheduled Timepoint	Statistics	Product		
		CA35	CM35	Cigarettes
Pre-Product Use	n	X	X	X
	Mean	XX	XX	XX
	SD	X.XX	X.XX	X.XX
	CV%	XX	XX	XX
	SEM	X.XX	X.XX	X.XX
	Minimum	XX	XX	XX
	Q1	X.X	X.X	X.X
	Median	X.X	X.X	X.X
	Q3	X.X	X.X	X.X
	Maximum	XX	XX	XX
	95% CI	XX-XX	XX-XX	XX-XX

CA35 = P4M3 Gen 2.0 Classic Auburn

CM35 = P4M3 Gen 2.0 Classic Menthol

SD = Standard deviation, CV% = Coefficient of variance, SEM = Standard error of mean, Q1 = 1st quartile, Q3 = 3rd quartile

CI = Confidence interval

PK Population = Subset of the safety population including all randomized subjects without major protocol deviations impacting the evaluability of the main objectives and for whom at least one nicotine PK parameter can be derived

Program: /CAXXXX/sas_prg/stsas/tab/ ADaM_program_name.sas DDMMYYYY HH:MM Status: DRAFT (Page X of Y)

Programmer Note: All scheduled timepoints will be included in the summary table.

Philip Morris Products S.A.
P4M3 Gen 2.0, P4-PK-04-US

████████ Statistical Analysis Plan Number CA34617

Tables 15.2.2.2.4 through 15.2.2.2.7 will have the following format:

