Table 15.2.2.2.4 Inferential Analysis of VAS Liking Assessment on PK Parameters (PK Population)

Product	PK Parameter	Sum Square of Linking Score	Total Sum Square	Percentage*	Standardized Effect of Liking Score
CA35	XXXXX	XXXX	XXXX	XX.XX	XX
	XXXXX	XXXX	XXXX	XX.XX	XX
	XXXXX	XXXX	XXXX	XX.XX	XX
CM35	XXXXX	XXXX	XXXX	XX.XX	XX
	XXXXX	XXXX	XXXX	XX.XX	XX
	XXXXX	XXXX	XXXX	XX.XX	XX
Cigarettes	XXXXX	XXXX	XXXX	XX.XX	XX
	XXXXX	XXXX	XXXX	XX.XX	XX
	XXXXX	XXXX	XXXX	XX.XX	XX

CA35 = P4M3 Gen 2.0 Classic Auburn

CM35 = P4M3 Gen 2.0 Classic Menthol

PK Population = Subset of the safety population including all randomized subjects without major protocol deviations impacting the evaluability of the main objectives and for whom at least one nicotine PK parameter can be derived

Sum square of liking score and total sum square are from ANCOVA model.

*percentage = The percentage of variance explained by product liking by the VAS-liking assessment which calculated as Sum square of product liking score divided by total sum square and multiply 100.

Standardized effect of product liking is defined as the mean effect divided by the square root of its variance which is the t-value of the product liking score effect.

Program: /CAXXXXX/sas_prg/stsas/tab/ ADaM_program_name.sas DDMMYY YYYY HH:MM Status: DRAFT (Page X of Y)

Programmer Note: PK parameters (C_{max}, T_{max}, and AUC_{0-infinity}) and the human puffing topography parameters (total number of puffs, total puff volume, and total puff duration) to be included.

Philip Morris Products S.A.
P4M3 Gen 2.0, P4-PK-04-US

████████ Statistical Analysis Plan Number CA34617

Table 15.2.2.3.1 will have the following format:

Table 15.2.2.3.1 Summary of Human Puffing Topography Parameters (PK Population)

Topography Parameter	Statistics	Product	
		P4M3 Gen 2.0	
XXXXXXX	n	X	X
	Mean	X.X	X.X
	SD	X.XX	X.XX
	CV%	X.X	X.X
	SEM	X.XX	X.XX
	Minimum	XX	XX
	Q1	X.X	X.X
	Median	X.X	X.X
	Q3	X.X	X.X
	Maximum	XX	XX
	95% CI	XX-XX	XX-XX

CA35 = P4M3 Gen 2.0 Classic Auburn

CM35 = P4M3 Gen 2.0 Classic Menthol

PK Population = Subset of the safety population including all randomized subjects without major protocol deviations impacting the evaluability of the main objectives and for whom at least one nicotine PK parameter can be derived

SD = Standard deviation, CV% = Coefficient of variance, SEM = Standard error of mean, Q1 = 1st quartile, Q3 = 3rd quartile

CI = Confidence interval

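### The pooled liking ANCOVA states no product term, so a product difference in both liking and nicotine uptake would be reported as an effect of liking

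*SAP*

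**What the plan says.** SAP 7.3 describes the first ANCOVA in words ("The model will include terms for sequence, period and product liking by the VAS-liking assessment") and in SAS code. In the code, product appears only in the BY statement and is absent from the CLASS and MODEL statements.

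The second ANCOVA is said to be like the first, with two changes: "it will be performed overall using mixed effects ANCOVA where the model will include, in addition, the subject as a categorical random effect". Protocol 12.7.2 has the same construction: "Another analysis of covariance (ANCOVA) will be conducted similarly at the exception that it will be performed overall using mixed effects ANCOVA". No code is given for the second model, and the SAP does not say which products are pooled. SAP section 11, which lists changes from the protocol analysis, adds no term.

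By contrast, the main PK model in SAP 6.5.1 names product explicitly: "sequence, period, product exposure as fixed effects and subject as a categorical random effect".

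The pooled PK results go to Table 15.2.2.2.5 and the pooled puffing results to Table 15.2.2.2.7. The shell in SAP 14.4 reports the percentage of variance explained by liking ("Sum square of liking score and total sum square are from ANCOVA model") and a standardized effect, "which is the t-value of the product liking score effect". Its programmer note lists C_max, T_max and AUC_0-infinity. With liking at 4, 10 and 15 minutes, that makes 3 × 3 = 9 pooled PK fits.

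**The concern.** Dropping the BY statement removes product from the model altogether. Each subject uses all three products, so product contrasts lie within subject and a random subject effect does not remove them. If one product is both better liked and delivers a different amount of nicotine, the model can represent that only through the liking slope.

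The pooled model is the only planned one that uses within-subject variation in liking, so the by-product tables cannot supply its answer. Protocol 4.2 and SAP 7.3 both describe the results as effects of liking. As stated, the model cannot tell whether liking goes with uptake or whether the better-liked product simply delivers a different amount.

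Both conditions are needed. There is no bias if the products do not differ in liking, or do not differ in PK.

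**Working it through.** The plan gives no figure of its own for this analysis, so there is none to reproduce.

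**Stated terms**

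| Model | Product | Other terms |
|---|---|---|
| Main PK ANOVA (SAP 6.5.1) | fixed effect | sequence, period, random subject |
| First liking ANCOVA (SAP 7.3) | BY variable | sequence, period, liking |
| Second liking ANCOVA (SAP 7.3) | none stated | sequence, period, liking, random subject |

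**Expected false slope.** Let cigarettes exceed both P4M3 variants by *g* mm in liking and by *d* = −ln(ratio) in ln C_max, where ratio is P4M3:cigarettes. Let *s* be the within-subject liking SD, and let liking have no true effect. Over one subject's three periods:

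- the expected within-subject cross-product of liking and ln C_max is 2gd/3;
- the expected within-subject sum of squares of liking is 2g²/3 + 2s².

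The slope per mm is therefore approximately g·d / (g² + 3s²).

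**Inputs from Protocol 12.2.1 and the design**

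- GCV 80%, so ln variance = ln(1 + 0.8²) = 0.495.
- Correlation 0.8, so between-subject variance = 0.8 × 0.495 = 0.396 and within-subject variance = 0.099.
- C_max geometric means: cigarettes 12 (range 11 to 13), P4M3 11 (range 9.4 to 12).
- 36 subjects, 6 sequences, 3 periods.

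**Assumptions not in the documents**

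- Cigarettes are in the pool.
- g = 10 to 30 mm, equal for both variants.
- Between-subject liking SD 10 mm; s = 15 to 25 mm.

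**Closed form at the corners**

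- 11/12, d = 0.0870: g = 10, s = 25 gives 0.870/1975 = 0.00044 per mm; g = 30, s = 15 gives 2.610/1575 = 0.00166 per mm.
- 9.4/13, d = 0.3242: the same corners give 3.242/1975 = 0.00164 and 9.727/1575 = 0.00618 per mm.

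**Simulation without product.** There were 3,000 trials per scenario, with random subject fitted by the Type 3 method of moments. The percentage is the Type 3 liking sum of squares over the corrected total. Ranges run over g and s.

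| C_max ratio | Slope, ln units per 10 mm (closed form) | Mean t | % of variance | Absolute t beyond the 5% cut-off |
|---|---|---|---|---|
| 11/12 = 0.92 | 0.0044 to 0.0166 | 0.32 to 1.03 | 0.23 to 0.41 | 6 to 17% |
| 11/13 = 0.85 | 0.0085 to 0.0318 | 0.54 to 1.95 | 0.27 to 0.96 | 8 to 48% |
| 9.4/12 = 0.78 | 0.0124 to 0.0465 | 0.79 to 2.77 | 0.37 to 1.81 | 11 to 79% |
| 9.4/13 = 0.72 | 0.0164 to 0.0618 | 0.96 to 3.54 | 0.49 to 2.94 | 16 to 94% |

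The simulated slopes match the closed form. If P4M3 delivers more (12/11 = 1.09), the sign reverses: mean t −0.3 to −1.0, with 6 to 17% beyond the cut-off.

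**Controls without product.** A ratio of 1.0 gives 4 to 6% beyond the cut-off and a liking gap of 0 gives 5%, both with slope about 0.

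**With product as a fixed effect.** In all scenarios the mean t is within ±0.03, the percentage of variance is 0.18 to 0.21, and 4 to 6% fall beyond the cut-off.

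**Other fits.** REML with a between-subject liking SD of 15 mm and s = 15 mm, for gaps of 10, 20 and 30 mm, gives 5, 10 and 16% at 11/12 and 28, 76 and 93% at 9.4/13. The result does not depend on the estimator.

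**Puffing.** Protocol 7.8.2 records no topography for cigarettes, so only a CA35 versus CM35 difference could leak into that model. The documents do not allow its size to be estimated.

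**The case against.** The stated objective is to describe associations. A cross-product slope is a legitimate description, and under ad libitum use liking may be part of how a product affects uptake. Liking is also rated during or shortly after absorption, so even an adjusted slope is not a clean effect. This stands as a reason to keep an unadjusted association if one is wanted. It does not justify reporting that association, unlabelled, as an effect of liking.

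The pool is unstated. The exploratory objective names P4M3 only, and Protocol 12.2.1 plans one geometric mean for the two variants. If only CA35 and CM35 are pooled, the planned C_max difference is zero and the figures above do not apply. The shared shell has a Cigarettes row, so the question is open. This limits the size and adds a reason to specify the model.

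The distortion is small at the planning ratio. The largest figures pair the bottom of one quoted range with the top of another and need large assumed liking gaps. The study has no hypothesis, no significance level and no p-value in the shell, so the 5% cut-off is only a yardstick. The by-product ANCOVA is reported alongside. All of this stands and lowers the severity.

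The wording could be read as silent on product. Yet the first model is fully listed and only two changes are named, so a programmer following the text would fit no product term.

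Finally, adding product removes only the product confounding. The model would still blend between- and within-subject liking slopes and impose one slope on all products. That is true, and it is not a reason to leave product out.

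**Conclusion.** The concern holds. As worded, the pooled ANCOVA has no product term, and any joint product difference in liking and PK enters the liking results in Table 15.2.2.2.5. For C_max, on the stated assumptions about pool, liking gap and liking SD, the effect is modest at the planning ratio: mean t at most about 1 and at most 0.4% of variance, against 0.2% with product. It becomes substantial toward the edge of the protocol's own ranges, with mean t up to about 3.5 and 2.9% of variance. Nothing was calculated for T_max, AUC_0-infinity or puffing. The issue is confined to the exploratory Tables 15.2.2.2.5 and 15.2.2.2.7. It should be corrected, but it does not affect the main objective.

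**What to change.** In SAP 7.3, add product as a fixed class effect to the pooled model, state which products are pooled, and give the code without the BY statement:

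```
PROC MIXED data=<> method=type3;
class subject sequence period product;
model log(PK parameter) = sequence period product liking_score / solution;
random subject;
run;
```

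The Type 3 method gives the sums of squares on which the reported percentage is built. If REML with ddfm=KR is to supply the t-value, say so separately. If an unadjusted cross-product association is wanted, show it beside the adjusted one and label it.

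For puffing, use the same terms with CA35 and CM35 only, and state the scale, because the log scale is specified for PK alone ("The PK parameters will be transformed in the natural logarithmic scale").

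A layout point follows. The SAP says "Tables 15.2.2.2.4 through 15.2.2.2.7 will have the following format", which has a row per product. A pooled model gives one liking effect, and a by-product fit has one record per subject, so it cannot separate subject variance from residual. Tables 15.2.2.2.5 and 15.2.2.2.7 should therefore have one overall row per parameter. SAP section 14 already allows shells to change, so this is not a contradiction.

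The cost is one model term (2 df for PK with three products, 1 df for puffing), one code block and two shell edits. No new data are needed.

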8. HUMAN PUFFING TOPOGRAPHY

8.1 Data Collection

Human puffing topography (HPT) involves the measurement of each subject's unique way of using P4M3 Gen 2.0.

The MDEDR puffing topography device measures and records the flow rate and other per-puff parameters listed in [Table 8.1](#).

Table 8.1 Human Puffing Topography Parameters Per-Puff

Description	Variable	Unit
Puff number	N_i	
Puff volume	V_i	mL
Puff duration	D_i	s
Average puff flow	Qm_i	mL/s
Peak flow	Qc_i	mL/s
Inter puff interval	I_i	s
Sum of I_i and D_i	DF_i	s
Peak flow position	$PosQc_i$	%

From the per-puff parameters, per-product experience parameters, representing average or total values per product, will be derived as in [Table 8.2](#).

Table 8.2 Human Puffing Topography Parameters Per-Product Use Experience

Description	Variable	Formula	Unit
Total number of puffs	NPC	$\sum N_i$	
Total puff volume	TVOL	$\sum V_i$	mL
Average puff volume	AvgVi	$\sum V_i / NPC, i=1 \dots NPC$	mL
Average puff duration	AvgDi	$\sum D_i / NPC, i=1 \dots NPC$	s
Total puff duration	TDi	$\sum D_i$	s
Average flow	AvgQmi	$\sum Qm_i / NPC, i=1 \dots NPC$	mL/s
Average peak flow	AvgQci	$\sum Qc_i / NPC, i=1 \dots NPC$	mL/s
Total inter puff interval	Tli	$\sum I_i$	s
Average inter puff interval	Avgli	$\sum I_i / NPC, i=1 \dots NPC$	s
Total puffing duration	TDFi	$\sum DF_i$	s
Puff Frequency	PFeq	$NPC/TDF_i/60$	

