2. OBJECTIVES AND ENDPOINTS

Main Objective and Endpoints:

The main objective of this study is:

1. To describe the plasma concentration-time profile of nicotine and derived pharmacokinetic (PK) parameters of 2 variants of P4M3 Gen 2.0 and cigarettes from 6 minutes *ad libitum* use.

Related Endpoints (Day 1 to Day 3):

- Background-corrected maximum plasma concentration [C_{max}]
- Background-corrected time to the maximum concentration [T_{max}]
- Area under the background-corrected concentration-time curve (AUC) from start of product use (T_0) to 2 minutes, to 4 minutes, to T_{max} , to 10 hours, to time of last quantifiable concentration and extrapolated to infinity [AUC_{0-2min} , AUC_{0-4min} , AUC_{0-Tmax} , AUC_{0-10h} , AUC_{0-last} , $AUC_{0-infinity}$]

Maximum ratio of background-corrected concentration over time, from T_0 (excluded) to T_{max} (included) [$\max(C_t/t)_{t \in [0, T_{max}]}$]

Secondary Objective and Endpoints:

The secondary objectives of this study are:

1. To describe pharmacodynamic (PD) effects (subjective effects and related behavioral assessments) of 2 variants of P4M3 Gen 2.0 and cigarettes from 6 minutes *ad libitum* use.

Related Endpoints (Day 1 to Day 3):

- Score from cigarette craving by the visual analog scale (VAS)-craving assessment
- Score from product evaluation by Assessment of Behavioral Outcomes related to Tobacco and nicotine products (ABOUT)-Product experience questionnaire
- Score from product liking by the VAS-liking assessment

2. To describe human puffing topography (HPT) of 2 variants of P4M3 Gen 2.0 from the 6 minutes *ad libitum* use.

Related Endpoints (Day 1 to Day 3):

- Per-puff parameters and per-product use experience parameters from the MDEDTR puffing topography device for 2 variants of P4M3 Gen 2.0

3. To describe the extent of product use from 2 variants of P4M3 Gen 2.0 from the 6 minutes *ad libitum* use.

Related Endpoints (Day 1 to Day 3):

- Amount of nicotine delivered derived from the weighing of P4M3 Gen 2.0 Cartridge before and after use

Philip Morris Products S.A.
P4M3 Gen 2.0, P4-PK-04-US
[REDACTED] Statistical Analysis Plan Number CA34617

4. To evaluate the safety and tolerability during the study.

Related Endpoints (From Enrollment to End-of-Study [EOS]):

- Incidence of adverse events (AEs) and serious adverse events (SAEs)
- Incidence of P4M3 Gen 2.0 product events including malfunction/misuse
- Changes in physical examination from baseline

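### SAP Table 8.2 drops the bracket from the puff frequency formula, making it 3600 times smaller than the protocol's; the puff count it uses should also be defined explicitly

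*SAP*

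**What the plan says.** SAP section 8.1 lists the variables recorded for each puff in Table 8.1 and then says: "From the per-puff parameters, per-product experience parameters, representing average or total values per product, will be derived as in" Table 8.2. SAP section 8.2 refers back to the formulas in Table 8.2 for the per-subject summaries, so that table is the working specification.

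Four rows of Table 8.2 matter here:

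- "Total number of puffs" (NPC) is the sum of Ni. Table 8.1 labels Ni only as the puff number, with no unit or further definition.
- Average puff volume, puff duration, flow, peak flow and inter-puff interval are each a sum over i = 1…NPC divided by NPC.
- "Total puffing duration" (TDFi) is the sum of DFi, in seconds.
- "Puff Frequency" (PFeq) is NPC/TDFi/60, with no bracket and no unit.

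Protocol Table 13 (section 12.6.2) and Appendix D contain the same set of parameters. They also define NPC as the sum of Ni, but give puff frequency as NPC/(TDFi/60). Their average inter-puff interval sums Qci, the peak flow; the SAP sums Ii, the interval itself. SAP section 11, which lists changes from the protocol's analysis, mentions neither difference.

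**The concern.** The protocol divides seconds by 60 to get minutes and then divides the puff count by the minutes. Without the bracket, the SAP divides the count by seconds and then by 60 again. The result is puffs per sixtieth of a second, a rate nobody would report. Because the row carries no unit, nothing in the table alerts a programmer to the slip.

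The row for NPC also depends on what Ni holds. If Ni were stored as 1, 2, 3 and so on, adding it up would not give the number of puffs, and every quantity divided by NPC would be wrong by an amount that differs between subjects.

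Puffing topography is a secondary objective. All per-product parameters go into Table 15.2.2.3.1, its by-sex version and the listings. Total number of puffs is also in in-text Table 9 and is one of three outcomes in the liking models of SAP section 7.3 ("total number of puffs, total puff volume, and total puff duration").

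**Working it through.** The documents give no numerical value to reproduce, so the check is algebra with an illustration.

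**Inputs.** The formulas are those of SAP Tables 8.1 and 8.2, protocol Table 13 and Appendix D. TDFi is in seconds in all of them. For illustration TDFi is set to 360 s, from the planned "6 minutes *ad libitum* use". The number of puffs is not given anywhere, so a range of 5 to 30 is assumed.

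**Puff frequency.**

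- Protocol: NPC/(TDFi/60) = 60 × NPC/TDFi.
- SAP, left to right: NPC/TDFi/60 = NPC/(60 × TDFi).
- Ratio, protocol to SAP: 60 × 60 = 3600, whatever NPC and TDFi are.

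With TDFi = 360 s and NPC taken as the true count n:

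| n (assumed) | Protocol, n/(360/60) | SAP, n/360/60 |
|---|---|---|
| 10 | 1.67 | 0.000463 |
| 15 | 2.50 | 0.000694 |
| 20 | 3.33 | 0.000926 |
| 30 | 5.00 | 0.00139 |

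The factor is the same for everyone, so relative comparisons between CA35 and CM35 would survive. The reported values would not.

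**Total number of puffs.** If Ni equals 1 for each puff, the sum is n and the table is right. If Ni is the sequence number, the sum is 1 + 2 + … + n = n(n+1)/2. NPC is then inflated by (n+1)/2, and each of the five averages is multiplied by 2/(n+1). With an assumed true mean puff volume of 50 mL:

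| n (assumed) | Sum of 1…n | NPC inflated by | Averages multiplied by | 50 mL becomes |
|---|---|---|---|---|
| 5 | 15 | 3.0 | 0.333 | 16.7 mL |
| 10 | 55 | 5.5 | 0.182 | 9.1 mL |
| 15 | 120 | 8.0 | 0.125 | 6.25 mL |
| 20 | 210 | 10.5 | 0.095 | 4.8 mL |
| 30 | 465 | 15.5 | 0.065 | 3.2 mL |

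Unlike the frequency factor, this one depends on each subject's own puff count. It would therefore distort product comparisons and, because n(n+1)/2 is not linear in n, the liking-model results for total number of puffs. Puff frequency would inherit the same inflation. Total volume, total puff duration and total interval do not use NPC and are right on either reading.

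**Average inter-puff interval.** The protocol's sum of Qci is in mL/s, while the row's unit is seconds. The SAP's sum of Ii has the right unit.

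**The case against.** The strongest reply concerns NPC. Neither document says that Ni is a running index; the subscript i already does that job. The row is labelled as the total number of puffs, and the averages run over i = 1…NPC. Under the sequence-number reading, 15 puffs would give NPC = 120 and the averages would need V1 to V120, which do not exist. A count was plainly intended, and a sensible programmer would probably count. This stands: a reader might infer that the total number of puffs and all five averages are certainly wrong, but the documents do not establish that. The definition is also the protocol's own, not something the SAP introduced.

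Second, a reader might infer that the factor of 3600 reaches Table 9 and the liking models. It does not. Those use only total number of puffs, total puff volume and total puff duration; puff frequency is in neither. Two of the three do not involve NPC at all.

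Third, the sponsor's topography group validates the puff data under its own procedures before per-product parameters are calculated (protocol 7.8.2), and a frequency of 0.0007 would look odd to anyone reviewing the output. Both may catch the error, but neither corrects the formula, and SAP section 8.2 points to Table 8.2.

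Last, a bracket lost when the SAP was converted to text cannot be excluded entirely, although both protocol tables keep theirs. One look at the typeset table settles it.

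**Conclusion.** The puff frequency formula in SAP Table 8.2 is wrong as written. It is 3600 times smaller than the protocol's, with no assumption beyond ordinary left-to-right division, and the departure is undeclared. It affects one descriptive secondary parameter, in Table 15.2.2.3.1, its by-sex version and the listings.

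The NPC definition is ambiguous rather than demonstrably wrong. The 3.0- to 15.5-fold inflation for 5 to 30 puffs holds only if Ni is read as a sequence number; only then do the five averages, Table 9 and the liking models suffer.

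The protocol's use of Qci in the average inter-puff interval is a slip that the SAP has already put right, so it changes no result.

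A reader might infer a threat to the study's conclusions. The documents do not support that: the study tests no hypothesis, topography is summarised descriptively apart from the exploratory liking models, the per-puff data allow recalculation, and the main PK objective does not use these formulas. This is a minor correction, worth making before programming.

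**What to change.** 1. In SAP Table 8.2, write PFeq = NPC/(TDFi/60) and give the unit as puffs/min.
2. In SAP Table 8.2, protocol Table 13 and protocol Appendix D, replace the sum of Ni with the count of valid puffs. Taking the maximum Ni instead is not safe: protocol 7.8.2 has invalid data discarded, so the remaining numbers may have gaps.
3. In protocol Table 13 and Appendix D, change the average inter-puff interval to the sum of Ii divided by NPC, for consistency with the SAP only.

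These are text edits. They need no new data and no change to the analysis.
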